8.9.1 Analysis of Primary Efficacy Variable

The primary efficacy analysis is of OS. OS rates will be assessed using the Kaplan Meier approach. Quartiles of survival time will be presented and 95% CIs will also be calculated on the quartiles for each treatment group. A log-rank (two-sided) test will be used to compare OS between the two treatment groups.

The hazard ratio (HR) and corresponding two-sided 95% CI for the treatment effect will be computed using Cox proportional hazards model.

Plots of the Kaplan-Meier curves will be provided for each treatment group.

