#### Analysis of secondary efficacy endpoints

Comparison between treatment groups for all secondary endpoints will be conducted at the final analysis with a two-sided alpha of 0.05.

Time to event endpoints (ie, TTP, TTSP, Time to worsening of PVT) will be compared between treatment arms using a log-rank test. Tumor response rates will be compared between treatment arms using the continuity adjusted Newcombe-Wilson test. The

FACT-Hep score will be compared between treatment arms using a mixed linear model with baseline score and the relative time from baseline as covariates.

Safety Analysis: All patients who received study treatments at least once will be included in the safety analysis. All adverse events will be reported according to the National Cancer Institute Common Terminology Criteria for Adverse Events v 4.0 (CTCAE) grades and coded using the Medical Dictionary for Regulatory Activities (MedDRA). The incidence of treatment-emergent adverse events (events which were not present at baseline or worsened in severity following the start of treatment) will be summarized according to MedDRA primary system-organ class (SOC) and preferred term . Laboratory values will be summarized by treatment group over time and overall.

Poolability and Other Analysis: Multivariate Cox regression analysis of time-to-event efficacy endpoints will be conducted on stratification criteria and other factors such as age, gender, duration of disease prior to randomization.

As a sensitivity analysis, to address the poolability of data across regions (ie, Europe, North America, Asia), study sites and gender, a Cox regression analysis of the primary efficacy endpoint, OS, will be conducted with factors of region, study site and gender, and to determine the impact of these factors on OS. Note: region and study site will not be included simultaneously in the model due to collinearity.

Should the impact of region, site or gender on OS be statistically and clinically relevant, the reasons for the observed differential treatment effect, such as patient demographic or clinical characteristics, will be investigated and reported. If the poolability of OS results are in direct question as a result of this sensitivity analysis, the primary endpoint (OS) will also be analyzed separately by region, site or gender.

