### 10.2.5 OTHER ANALYSES

The number of randomized patients, the number of patients treated, the number of patients in each analysis population will be summarized. Also the number of patients discontinuing from active treatments and reasons for discontinuation will be summarized. In the same manner the number of patients discontinuing follow up and reasons for discontinuations will be reported.

Listings of reasons for discontinuation from active treatments, from follow up, and reasons efficacy data cannot be evaluated in PPP will be also provided.

Duration of follow up will be described by descriptive statistics such as median and interquartile range.

Demographic, patient and disease characteristics will be listed and summarized using appropriate descriptive statistics.

Multi-variate Cox regression analysis of time-to-event efficacy endpoints will be conducted on AFP level, age, gender, naïve or recurrent disease, HCC diagnosis present at first oncology diagnosis, prior treatment, geography to determine the impact of these factors on trial endpoints.

As a sensitivity analysis, to address the poolability of data across regions (ie, Europe, North America or Asia), study sites and gender, a Cox regression analysis of the primary efficacy endpoint, OS, will be conducted with factors of region, study site and gender, and to determine the impact of these factors on OS. Note: region and study site will not be included simultaneously in the model due to collinearity.

Should the impact of region, site or gender on OS be statistically and clinically relevant, the reasons for the observed differential treatment effect, such as patient demographic or clinical characteristics, will be investigated and reported. If the poolability of OS results are in direct question as a result of this sensitivity analysis, the primary endpoint (OS) will also be analyzed separately by region, site or gender. The specific

mechanism of merging low enrolling study sites into virtual sites for purposes of analysis will be detailed in the Statistical Analysis Plan.

AFP levels at Q8 week visits for patients with AFP >400ng/mL at screening will be compared, in separate analyses, to RECIST v 1.1, mRECIST and EASL response criteria to correlate biological and radiological response to explore the use of variations in AFP as a confirmation of radiological response.

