4.2 Method of Assignment of Patients to Treatment Groups

Patients will be randomized 1:1 to study treatment, either the Control arm or the Treatment arm.

If a patient is determined to be eligible to participate in the trial, the study site will contact the central randomization office via telephone or by internet where randomization will be determined using assignment by a computer-generated randomization scheme. Upon randomization, each patient will be assigned a subject identity code consisting of the protocol number, the site number (e.g. 01) and a patient identifier number (e.g. 001).

A centralized randomization schedule was generated by a statistician in the Chiltern International Biometrics department who is not associated with the conduct or analysis of the study, using a validated system. In order to create a balance between study arms, patients are stratified at randomization based on the following:

- AFP \(\leq 400 \) ng/mL or \(\rightarrow 400 \) ng/mL
- Participating trial site

The randomization will be performed using the Balance system with Medidata. Each eligible patient will be assigned to the next sequential randomization number within the specified stratification combination and will receive the corresponding study treatment. The randomization schedule will be kept strictly confidential and accessible only to authorized persons. Only when the study has been completed, the protocol violations determined, and the study database locked will the randomization schedule be made available for analysis.

Patients randomized to the Control arm or the Treatment arm, unable to receive their planned study treatment, will continue to be followed under their assigned study arm for the purpose of the intent-to-treat analysis.

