5 CHANGES IN THE CONDUCT OF THE STUDY OR PLANNED ANALYSES

This SAP is based on protocol version 3.0 dated 08 August 2014. Due to challenges with patient recruitment the study was terminated prematurely; therefore, only a final analysis will be performed without any interim analyses..

Protocol section 10.2.3.2 states that time to progression (TTP) will be calculated as the interval between the randomization date and the date of first disease progression as defined by the respective criteria noted below, death for any cause or of last contact for patients alive. However, death will not be considered in the calculation of TTP. Section 6.4.2.1 of this SAP explains how TTP will be analyzed.

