7.2 Adjustments for Covariates

The following covariates will be included, one at a time, in univariate Cox regression analysis of time-to-event efficacy endpoints, including OS

Stratification factor (AFP \u226400 ng/mL vs \u226400 ng/mL

Notes:

Stratification factor of AFP according to the master file will be used even if the stratification factor was incorrectly recorded at randomization.

Site is also a stratification factor in this study. However, due to early termination of the study and small number of subjects per site, site will not be included as a covariate in this analysis since it would likely result in non-convergence of the model.

- ECOG status at baseline
- Age
- Gender
- Region (North America, Europe, Asia)
- Naïve or recurrent disease
- HCC diagnosis present at first oncology diagnosis
- Prior oncologic treatment for HCC (none, local regional therapy, prior resection, or systemic treatment)
- Duration from date of initial diagnosis of HCC to randomization
- Percent Tumor replacement at baseline
- HCC etiology (alcoholism, hepatitis B, hepatitis C, afloxatin-contaminated food, non-alcoholic cirrhosis, diabetes and other (including unknown))
- ALBI score (1, 2 or 3) at baseline

These covariates will also be included, one at a time, in a logistic regression analysis of binary efficacy endpoints.

All factors in the univariate models with a two-sided p-value <0.15 will be included in a multivariate analysis to determine the impact of these factors.

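### The OS and secondary log-rank tests ignore the AFP randomisation stratum, and SAP 7.2 lets AFP drop out of a multivariable model in which the protocol includes it

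*SAP*

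**What the plan says.** SAP 4.2 describes the allocation: "In order to create a balance between study arms, patients are stratified at randomization based on the following", and the factors listed are AFP (≤400 vs >400 ng/mL) and trial site. Protocol 9.2.15 gives the same two factors.

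For the primary endpoint, SAP 8.9.1 says "A log-rank (two-sided) test will be used to compare OS between the two treatment groups", with the hazard ratio from a Cox model. It names no strata or covariates. The log-rank tests in SAP 8.9.2 for TTP, worsening of PVT, TTSP and deterioration in quality of life name none either. The protocol's log-rank test for OS (synopsis and 10.2.3.1) is likewise given without strata.

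AFP enters only through SAP 7.2. Twelve covariates, AFP among them, go singly into Cox models, and treatment is not named as a model term. Then: "All factors in the univariate models with a two-sided p-value <0.15 will be included in a multivariate analysis". AFP is not exempt. Site is left out because, with few patients per site, "site will not be included as a covariate in this analysis since it would likely result in non-convergence of the model". For AFP, 7.2 says only which value to use: "Stratification factor of AFP according to the master file will be used even if the stratification factor was incorrectly recorded at randomization".

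The protocol has no p-value screen. Its synopsis says "Multivariate Cox regression analysis of time-to-event efficacy endpoints will be conducted on stratification criteria and other factors such as age", and 10.2.5 says "Multi-variate Cox regression analysis of time-to-event efficacy endpoints will be conducted on AFP level, age, gender". SAP 5 records the early stop ("Due to challenges with patient recruitment the study was terminated prematurely; therefore, only a final analysis will be performed without any interim analyses") and a change to TTP, but not the screen.

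**The concern.** A factor judged important enough to stratify the allocation would normally be carried into the analysis. Protocol 5.3 itself reports that alphafetoprotein level predicted survival in a large single-centre cohort, although it gives no hazard ratio and no 400 ng/mL cut-off, and that cohort was broader than this trial's population.

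Two things follow.

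- **Primary and secondary tests.** Stratified allocation balances AFP between arms, but an unstratified log-rank variance still counts AFP as noise. If AFP is clearly prognostic, the test tends to be conservative and loses power.
- **Multivariable model.** The p<0.15 screen can remove AFP by chance, most readily in a trial that stopped early. The plan then guarantees no AFP-adjusted treatment effect in any output, and the departure from the protocol goes undeclared. The reason given for leaving out site does not carry over to a two-level factor.

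**Working it through.** **1. The plan's own design figure.** Inputs from SAP 4.4 and Protocol 10.2.3.1: 250 deaths, medians of 9 and 13 months (hazard ratio 9/13 = 0.692), two-sided alpha 0.05, looks at 125, 188 and 250 deaths, spending function 0.05·t^1.5.

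- Cumulative alpha spent: 0.0177, 0.0326, 0.0500.
- Nominal two-sided boundaries: 0.0177, 0.0229, 0.0321 (stated 0.0177, 0.0228, 0.0322).
- Drift at the last look: √(250/4)·|ln(9/13)| = 7.906 × 0.3677 = 2.907.
- Group-sequential power: 79.9% at 9/13 and 80.7% at 0.69 (stated 80%).
- A single look at 0.05: Φ(2.907 − 1.960) = 82.8%.

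The design reproduces. It makes no allowance for AFP.

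**2. Stratified against unstratified at the planned size.** The documents give neither the share of patients with AFP >400 nor the AFP effect on survival. Assumed: a share of 30% or 50% and an AFP hazard ratio of 1.0 to 2.5. Simulation: 320 patients, 250 deaths, treatment hazard ratio 9/13, one look at 0.05 (1,500 trials per cell).

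| AFP hazard ratio | Power, unstratified | Power, stratified by AFP |
|---|---|---|
| 1.0 | 83–85% | 82–85% |
| 1.5 | 81–84% | 81–85% |
| 2.0 | 78–80% | 82–84% |
| 2.5 | 76% | 82–84% |

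Type I error at an AFP hazard ratio of 2.5 (3,000 trials per cell) is 3.3–3.8% unstratified; the stratified test runs at 4.1–5.4% throughout.

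**3. Smaller sizes.** The number randomised at termination is also not given, so N was varied. Exponential survival, control median 9 months, 50% with AFP >400, exact balance within AFP, censoring uniform over 12–54 months, 4,000 trials per cell:

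| AFP hazard ratio | N | Unstratified | Stratified | Difference (points) |
|---|---|---|---|---|
| 2.0 | 40 | 13.9% | 16.1% | +2.2 |
| 2.0 | 80 | 27.2% | 30.7% | +3.5 |
| 2.0 | 150 | 49.4% | 53.0% | +3.6 |
| 2.5 | 80 | 24.7% | 31.4% | +6.7 |
| 2.5 | 150 | 44.3% | 51.8% | +7.5 |

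A wider grid used N = 40 to 320 and shares of 30% and 50%. At the 50% share it added blocks of 4 within AFP by 20 sites, 10% of patients dropped after randomisation, and shorter censoring of 3–30 months. The change in power from stratifying is:

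- AFP hazard ratio 1.0: −1.0 to −0.2 points
- 1.5: −0.2 to +1.4
- 2.0: +1.3 to +5.8
- 2.5: +1.9 to +9.4

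Unstratified type I error in this grid is 3.9–5.1% at an AFP hazard ratio of 2.0 and 3.4–4.9% at 2.5. With AFP-by-site blocks at N=40 it is 4.6–6.2%, so conservatism is not assured. The stratified test runs at 4.5–6.0%. Monte Carlo standard error on these rates is about 0.2–0.4 points.

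**4. Chance that AFP fails the p<0.15 screen.** With d deaths, share p with AFP >400 and AFP hazard ratio h, the chance of passing is Φ(a − 1.440) + Φ(−a − 1.440), where a = √(d·p(1−p))·ln h. For d = 50, p = 0.5, h = 1.5: a = 3.536 × 0.4055 = 1.434, so the chance is 0.498 + 0.002 = 0.500, and AFP fails half the time. Chance of failing over p = 0.3 and 0.5:

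| AFP hazard ratio | 15 deaths | 30 | 50 | 100 |
|---|---|---|---|---|
| 1.5 | 73–75% | 62–66% | 50–55% | 28–34% |
| 2.0 | 54–58% | 32–38% | 16–21% | 2–4% |

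Simulated by N on the wider grid, failure is 62–68% (N=40), 43–52% (N=80) and 22–33% (N=150) at a hazard ratio of 1.5, and 32–43%, 10–19% and 1–4% at 2.0.

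**The case against.** The protocol's primary test has no strata either, so on that test the SAP departs from nothing. An unstratified log-rank test after stratified allocation is valid, and the unstratified hazard ratio is a legitimate marginal quantity. Replacing the primary test after an open-label trial has stopped carries its own risk, and adding the stratified test as a sensitivity analysis would give the same information. The gain depends on an assumed AFP effect and is negligible at 1.5 or below.

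The screen may also do little harm on average. In trials where AFP fails it, unstratified and stratified power are nearly equal: 19.3% vs 18.8% (N=40, AFP hazard ratio 1.5), 32.5% vs 32.6% (N=80, 1.5) and 20.2% vs 20.1% (N=40, 2.0). The protocol's Cox model is meant to assess the factors, and the protocol does not name treatment in it. Finally, the survival code in SAP Appendix 2 cannot be read in the available text, so the absence of strata is inferred from the prose.

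Most of this stands as a limit on size. The point concerns efficiency and reporting, not validity. The near-equality is an average, however: at N=40 the two log hazard ratios differ between individual trials with a standard deviation of about 0.08. None of it explains why a stratification factor is screened by p-value when the protocol does not do so, or why SAP 5 omits the change. The timing risk is met by a dated entry made before by-arm data are seen, with the protocol's test retained alongside.

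**Conclusion.** The point holds as a recommended change rather than a critical fault. In the readable text the tests and the OS hazard ratio are unstratified by a factor used to randomise, and the p<0.15 screen on AFP is an undeclared departure from the protocol.

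The first part costs little if AFP is weakly prognostic and several points of power if its hazard ratio is 2.0 or more. Stratifying would not recover power lost to missing deaths. The second part does not depend on the power gain: with few deaths, AFP can easily be screened out by chance, leaving no AFP-adjusted treatment effect reported. All sizes rest on assumed values for the AFP effect, the share with AFP >400, the censoring pattern and the number of patients.

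**What to change.** - **SAP 8.9.1 and 8.9.2:** stratify the log-rank tests and Cox hazard ratios by AFP (≤400 vs >400 ng/mL, master-file value as in 7.2), without site. Report the protocol's unstratified analysis as a sensitivity analysis.
- **SAP 7.2:** name treatment as a model term, and keep treatment and AFP in every multivariable model whatever their univariate p-values.
- **SAP 5:** record both points as dated changes from the protocol, with reasons, before database lock and before any review of outcomes by arm.
- **SAP Appendix 2:** make sure the survival code and the prose agree on strata.

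The cost is a STRATA statement, a few lines of text and a justified entry in SAP 5. AFP is needed to randomise, so no new data are required. If AFP proves not to be prognostic, the price is about 1 point of power or less.

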8.9.2 Analysis of Secondary Efficacy Variables

The secondary efficacy endpoints for this study are:

- Time to Progression (TTP)
- Time to Worsening of PVT
- Time to Symptomatic Progression (TTSP)
- Tumor Response Rate (ORR and DCR)
- Quality of Life (FACT-Hep)

8.9.2.1 Time to Progression

TTP rates will be derived and quartiles on the rates will be presented. 95% CIs will be calculated on the quartiles for each treatment group under RECIST 1.1, mRECIST, and EASL criteria. A log-rank (two-sided) test will be used to compare TTP between the two treatment groups at a 0.05 significance level. Plots of the Kaplan-Meier curves will be provided for each treatment group.

8.9.2.2 Time to Worsening of PVT

Time to worsening PVT rates will be derived and quartiles on the rates will be presented. 95% CIs will be calculated on the quartiles. A log-rank (two-sided) test will be used to compare time to worsening PVT between the two treatment groups at a 0.05 significance level. Plots of the Kaplan-Meier curves will be provided for each treatment group.

8.9.2.3 Time to Symptomatic Progression

TTSP rates will be derived and quartiles will be presented and 95% CIs will be calculated on the quartiles for each treatment group. A log-rank (two-sided) test will be used to compare TTSP between the two treatment groups at a 0.05 significance level. The HR and corresponding 95% CI will be computed. Plots of the Kaplan-Meier curves will be provided for each treatment group.

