Salem et al demonstrated the tolerability of TheraSphere in treatment of patients with HCC and branch PVT11 and patients with unresectable HCC12. Salem et al13 recently published their long-term experience of TheraSphere in the treatment of patients with HCC. In this report, patients with HCC (n=291) were treated with TheraSphere as part of a single-center, prospective, longitudinal cohort study. Toxicities were recorded using the Common Terminology Criteria version 3.0. Response rate and time to progression (TTP) were determined using World Health Organization (WHO) and European Association for the Study of the Liver (EASL) guidelines. Survival by stage was assessed. Univariate/multivariate analyses were performed. A total of 526 treatments were administered (mean, 1.8; range, 1-5). Toxicities included fatigue (57%), pain (23%), and nausea/vomiting (20%); 19% exhibited grade 3/4 bilirubin toxicity. The 30-day mortality rate was 3%. Response rates were 42% and 57% based on WHO and EASL criteria, respectively. The overall TTP was 7.9 months (95% confidence interval, 6-10.3). Survival times differed between patients with Child-Pugh A and B disease (A, 17.2 months; B, 7.7 months; P = .002). Patients with Child-Pugh B disease who had portal vein thrombosis (PVT) survived 5.6 months (95% confidence interval, 4.5-6.7). Baseline age; gender; performance status; presence of portal hypertension; tumor distribution; levels of bilirubin, albumin, and alphafetoprotein; and WHO/EASL response rate predicted survival. These investigators concluded that patients with Child-Pugh A disease, with or without PVT, benefited most from treatment. Patients with Child-Pugh B disease who had PVT had poor outcomes. TTP and overall survival varied by patient stage at baseline.

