#### 8.1 ELIGIBILITY CRITERIA

Patients must meet the following eligibility criteria:

- Patients over 18 years of age, regardless of race or gender
- Advanced stage HCC confirmed by histology (mandatory in non cirrhotic patients) or non-invasive criteria (EASL/AASLD) with branch PVT.
  - Either naïve or recurrent HCC after curative treatment (minimum 3 months from curative treatment - minor resection or local ablation) is acceptable
  - Branch PVT classified per modified Shi et al 2010^16 as Type I, Type II or Type IIIa (see Section 9.2.5).
- Unilobar disease which can include multifocal tumors if unilobar and if all nodules (including nodule associated with PVT) are treatable within a single TheraSphere treatment session
- Tumor volume ≤ 70% of liver volume (determined by visual estimation)
- Child-Pugh A
- At least one uni-dimensional HCC target lesion assessable according to the RECIST v1.1 criteria by CTscan or MRI
- No confirmed extrahepatic metastases. Patients with indeterminate hepatic hilar lymph nodes up to 2.5 cm in greatest dimension, or with indeterminate lung nodules (single lesion between 1 − 1.5 cm, or multiple smaller lesions with a total diameter ≤ 2 cm) may be included if metastatic disease is deemed unlikely
- 8. No known contraindications to standard-of-care sorafenib including allergic reaction, pill swallowing difficulty, uncontrolled hypertension or history of cardiac disease (according to sorafenib package insert and country-specific policies, may include evidence of severe or uncontrolled systemic diseases, cardiac arrhythmias (requiring anti-arrhythmic therapy or pace maker), congestive cardiac failure >New York

Heart Association class 2, myocardial infarct within 6 months, prolonged QT/QTc >450ms), or laboratory finding that in the view of the investigator makes it undesirable for the patient to participate in the trial, significant GI bleed within 30 days, renal failure requiring dialysis

- No evidence of hepatic vein invasion or caval thrombosis
- Cancer-related symptoms within the ECOG 0-1 category
- PLT ≥ 50 x10^3/µL
- WBC ≥ 1.5 x10³/µL
- AST/ALT ≤ 5 times the upper limit of normal (U/L)
- Creatinine ≤ 2.0 mg /dL
- 15. No evidence of pulmonary insufficiency or clinically evident chronic obstructive pulmonary disease.)
- No indication for any possible curative treatment after multidisciplinary assessment (surgery, ablation, transplantation)

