6.4.2.3 Time to Symptomatic Progression

TTSP is defined as the time from date of randomization to date of assessment of ECOG performance status ≥ 2 with or without tumor progression based on investigator assessment. Deterioration in performance status is to be confirmed at one subsequent evaluation 8 weeks later. The first date at which the ECOG performance status was ≥ 2 will be used as the end date in the TTSP analysis (assuming the next subsequent visit confirmed the deterioration).

TTSP (Months) = (Date of ECOG ≥ 2 – Date of Randomization + 1)/30.4375.The censoring is performed as follows:

- If a patient does not have a post baseline ECOG performance status, then the TTSP will be censored at the randomization date;
- 2) If a patient has post baseline ECOG assessment but did not have ECOG ≥2 then TTSP will be censored at the last post baseline ECOG performance status assessment date.

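### The TTSP log-rank test and hazard ratio name no adjustment for baseline ECOG, the starting value of the outcome, and the SAP 7.2 covariate screen does not guarantee one (minor, secondary endpoint)

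*SAP*

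**What the plan says.** **Endpoint.** SAP 6.4.2.3 dates TTSP at the first ECOG status of 2 or more, subject to this condition: "Deterioration in performance status is to be confirmed at one subsequent evaluation 8 weeks later". Patients who never reach ECOG 2 are censored at their last ECOG assessment. Death is not listed as an event.

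**Entry.** Protocol 8.1 requires "Cancer-related symptoms within the ECOG 0-1 category". SAP 6.3 includes ECOG among the baseline assessments.

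**Randomisation.** Protocol 9.2.15 and SAP 4.2 stratify by AFP (cut at 400 ng/mL) and by site, not by ECOG.

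**Treatment comparison.** SAP 8.9.2.3: "A log-rank (two-sided) test will be used to compare TTSP between the two treatment groups at a 0.05 significance level". Then: "The HR and corresponding 95% CI will be computed". No stratum or covariate is named for either.

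**Covariates.** SAP 7.2: "The following covariates will be included, one at a time, in univariate Cox regression analysis of time-to-event efficacy endpoints, including OS". One entry in the list is "ECOG status at baseline". The selection rule is: "All factors in the univariate models with a two-sided p-value <0.15 will be included in a multivariate analysis". The stated aim is to learn the impact of the factors. The section does not say that treatment is in these models, or that any of them supplies the reported treatment HR.

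**The concern.** A patient who enters at ECOG 1 is one grade from the event; a patient who enters at ECOG 0 is two grades away. Baseline ECOG is therefore likely to predict TTSP. Protocol 5.3 points the same way: in a published single-centre TheraSphere cohort, the predictors of survival included "Baseline age; gender; performance status; presence of portal hypertension". That outcome is survival rather than TTSP, and no effect size is given.

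Randomisation does not force ECOG balance, and SAP section 5 says the study stopped early over recruitment. In a small trial one arm can by chance hold clearly more ECOG 1 patients. An unadjusted comparison would then mix that imbalance with the treatment effect in the one dataset the sponsor has. In an open-label trial, leaving the adjustment unspecified also leaves room to choose it after results are known.

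**Working it through.** **1. The plan's own figure.** No power is stated for TTSP. The only design power is for OS: 80% with 250 deaths, HR 0.69, two-sided 0.05 and rho = 1.5 spending. Cumulative alpha at the first look is 0.05 × (125/250)^1.5 = 0.0177, as stated. The full group sequential calculation gives nominal p-values of 0.0177, 0.0229 and 0.0321 (stated 0.0177, 0.0228, 0.0322) and power of 80.7% at HR 0.69, or 79.9% at medians of 9 and 13 months. The OS design reproduces. It says nothing about TTSP.

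**2. Does SAP 7.2 secure an ECOG-adjusted effect?** Even if treatment is in the multivariate model, ECOG must first pass p<0.15, a cutoff of |z| = 1.44. Assume a true ECOG HR (1 v 0) of 2 and a 50:50 split. Then SE(log HR) ≈ 2/√events.
- 30 events: SE = 0.365, z = 0.693/0.365 = 1.90, so ECOG is dropped with probability Φ(1.44 − 1.90) ≈ 32%.
- 20 events: SE = 0.447, z = 1.55, so the probability is Φ(1.44 − 1.55) ≈ 46%.

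**3. Size of a chance imbalance.** The SD of the between-arm difference in ECOG 1 share is √(4p(1−p)/N). With p = 0.4 (assumed) it is 12.6, 9.8 and 5.5 points at N = 60, 100 and 320. With p = 0.5 and 20 per arm it is √(2 × 0.25/20) = 15.8 points. By a normal approximation, a difference of 20 points or more in either direction is 20/15.8 = 1.26 SD (about 21% of trials) at N = 40, 20/12.6 = 1.58 SD (about 11%) at N = 60, and 20/9.8 = 2.04 SD (about 4%) at N = 100.

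**4. Effect of a given imbalance when treatment does nothing.** Simulation, 3,000 runs per setting. Assumptions: exponential times, 40% ECOG 1, about two-thirds of ECOG 0 controls with an event, and a fixed 20-point excess of ECOG 1 in one arm.

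| N | ECOG HR | Mean HR, unadjusted | Mean HR, stratified | Rejection %, unadjusted / stratified |
|---|---|---|---|---|
| 60 | 1.5 | 1.07 | 0.99 | 5.6 / 4.9 |
| 60 | 2 | 1.15 | 1.00 | 6.4 / 5.3 |
| 60 | 3 | 1.22 | 1.00 | 8.3 / 4.9 |
| 100 | 1.5 | 1.08 | 1.00 | 5.9 / 5.2 |
| 100 | 2 | 1.15 | 1.00 | 7.4 / 5.3 |
| 100 | 3 | 1.21 | 1.00 | 11.5 / 5.3 |

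A 10-point excess gives a mean unadjusted HR of 1.02 to 1.10 over N = 60, 100 and 320. At N = 40, with a 20-point excess, rejection is 6–8% unadjusted against 6% stratified. Averaged over all randomisations, the unadjusted test rejects in 4.5 to 5.7% of null trials, so it keeps its level.

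**5. Power, unadjusted → stratified (%).** Assumed treatment HR for TTSP is 0.69. Rows A use the assumptions of step 4 without a fixed imbalance. Rows B use a 50:50 ECOG split, the OS planning hazard, and 42 months of accrual plus 12 months. Rows C add death as censoring at the OS planning rate, which leaves about 43% with events.

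| Setting | ECOG HR 1.5 | ECOG HR 2 | ECOG HR 3 |
|---|---|---|---|
| A, N = 60 | 20.9 → 20.2 | 18.4 → 19.6 | 18.3 → 21.5 |
| A, N = 100 | 30.8 → 31.6 | 29.4 → 32.1 | 26.7 → 32.2 |
| A, N = 320 | 74.4 → 75.3 | 70.8 → 76.5 | 67.0 → 78.1 |
| B, N = 40 | 17.8 → 17.3 | 17.4 → 17.5 | 13.9 → 17.2 |
| B, N = 320 | 83.3 → 85.0 | 79.8 → 84.6 | 70.6 → 84.2 |
| C, N = 40 | 11.0 → 10.3 | 11.0 → 10.9 | 10.1 → 10.4 |
| C, N = 320 | not run | 54.8 → 58.2 | 47.0 → 55.9 |

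Monte Carlo error is about 0.8 points or less. At 20 per arm the change is about -1 to +3 points, or -1 to +1 once death censors TTSP. Gains above about 6 points need both an ECOG HR near 3 and a sample of 200 or more (A at N = 200, ECOG HR 3: 46.5 → 57.9).

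**The case against.** A plain log-rank test is a legitimate choice, and the protocol pre-specified it for TTSP. OS, TTP and PVT worsening are handled the same way. The FACT-Hep model does adjust for its baseline score, but the closer comparator is time to deterioration in QoL, which also has an unadjusted log-rank test. The SAP tabulates baseline ECOG, so an imbalance would be visible. All of this stands, and it keeps the point small.

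Three stronger readings are tempting, and the documents do not support them.
- **That the plan ignores baseline ECOG for TTSP.** SAP 7.2 lists it for the time-to-event endpoints. The gap is that 7.2 does not promise an ECOG-adjusted treatment effect.
- **That the TTSP test is biased.** Under randomisation it holds its 5% level. The distortion is conditional on an imbalance that may not occur. Efficacy is analysed in treated rather than all randomised patients (SAP 8.9), but nothing in the documents ties that exclusion to ECOG.
- **That substantial power is lost.** Gains of 11 to 14 points appear only at the planned N = 320 with an ECOG HR of 3. The trial stopped short of its plan, and the documents give no ECOG effect on TTSP.

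The absence of adjustment is read from the wording of SAP 8.9.2.3. The survival code in SAP Appendix 2 is not legible in the text available, so a STRATA term there could not be checked.

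**Conclusion.** The point holds as a minor improvement to a secondary endpoint. As written, the TTSP comparison is unadjusted for the starting value of its own outcome, that value is not balanced by design, and the 7.2 screen may drop it (about 32 to 46% of the time with 20 to 30 events, if the true ECOG HR is 2).

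The ground for change is conditional. With a 20-point excess of ECOG 1 in one arm and no treatment effect, the unadjusted HR averages 1.07 to 1.22 and the stratified HR about 1.00. Power is not a material reason at about 20 per arm. These sizes rest on assumed ECOG HRs of 1.5 to 3, assumed ECOG shares of 40 to 50%, exponential times and assumed sample sizes; the SAP does not give the final number randomised.

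**What to change.** In SAP 8.9.2.3, before database lock, state that the TTSP log-rank test and Cox HR are stratified by baseline ECOG (0 v 1), whatever the SAP 7.2 screen shows. A Cox model containing treatment and baseline ECOG is an acceptable alternative for the HR. Report the unadjusted test and HR as a sensitivity analysis. In SAP 7.2, say whether treatment is in the covariate models.

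The cost is a sentence or two and one STRATA term, with no new data. A single two-level stratum should not raise the convergence problem for which 7.2 drops site. Two downsides should be accepted openly: the HR becomes conditional on ECOG, and in a very small sample with a weakly prognostic ECOG, stratifying may cost up to about 1 point of power (for example 20.9 to 20.2% at N = 60).
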